3.2.2.2 Clinical Laboratory Data

Blood samples will be collected for clinical laboratory (chemistry, hematology, urinalysis) at Screening, Weeks 2 and 16/Early Termination visits.

Table 3.2.2.2-1 Clinical Laboratory Tests

Hematology	Chemistry	Urinalysis	Additional Tests
Hemoglobin	Glucose [a]	Specific gravity	[REDACTED]
Hematocrit	Total bilirubin	pH	[REDACTED]
Leukocyte count (total)	Alanine aminotransferase	Glucose	[REDACTED]
Leukocyte count (differential)	Aspartate aminotransferase	Protein	[REDACTED]
Red blood cell count	Alkaline phosphatase	Blood	[REDACTED]
Platelet count	Blood urea nitrogen	Bilirubin	[REDACTED]
	Pregnancy (WOCBP at Screening)	Ketones	[REDACTED]
	Sodium		
	Potassium		
	Chloride		
	CO2		
	Creatinine		
	Calcium		
	Protein		
	Albumin		
	Anion GAP		
	GFR		

a. Clinical laboratories need not be fasting

3.2.2.3 Height, Weight, Vital Signs

Height will be collected only at the Screening visit. Weight and vital signs (i.e., body temperature, respiration rate, sitting radial pulse rate, and sitting systolic and diastolic blood pressures) will be obtained at the Screening Visit, Injection Visit (pre- and post-treatment), Weeks 1, 2, 4, 8, and 16/Early Termination, [REDACTED]

3.2.2.4 Physical Examination

A full physical examination, including neurological examination of the face, general appearance, skin, neck (including thyroid), eyes, ears, nose, throat, heart, lungs, abdomen, lymph nodes, and extremities will be conducted at Screening and pre-treatment at the Injection visit. Significant

physical examination findings that are present prior to investigational product administration are to be included on the Medical History page.

At post-treatment visits, the physical examination may be abbreviated, as deemed medically appropriate at the discretion of the Investigator. Significant physical examination findings which meet the definition of an adverse event will be recorded on the adverse event page post-treatment.

3.2.2.5 12-Lead ECG

At Screening, Week 2, and Week 16/Early Termination, a single standard supine 12-Lead ECG will be obtained after a subject has rested quietly for at least 10 minutes. The ECG data will be submitted to a central reader for measurement.

3.2.2.6 Injection Site Evaluation

The injection sites will be evaluated before injection and post-injection at Injection Visit (Day 1; to determine if there is an immediate reaction to the investigational product), and at follow-up Visits (Weeks 1, 2, 4, 8, and 16/Early Termination visit, if applicable). The assessment will be done as a global evaluation of the four injection sites reporting the presence or absence of: erythema, edema, burning or stinging (as described by the subject), itching (as described by the subject), bruising and drainage.

3.2.2.7 Foot and Ankle Examination

Examination for the foot includes ankle, toe, and subtalar range of motion, foot motor strength, location of pain, and examination of the heel fat pad and Tinel's sign. This will be performed at Screening, pre-treatment Injection, Weeks 1, 2, 4, 8, and 16/Early Termination visits. The presence of toe deformities, bunions, ulcers, and/or sores will be documented. The feet will be examined for signs of swelling, pitting edema, infection, or vascular abnormalities.

3.2.2.8 Concomitant Medications

Concomitant medications are any prescription or over-the-counter preparations used by subjects during participation in the trial. Use of concomitant medications will be recorded, beginning at the Screening Visit until the Week 16/Early Termination visit. The dose and dosing regimen of all prescription and non-prescription therapies and medications, including herbs, vitamins, or other nutritional supplements administered will be documented.

4 Statistical Methods

All statistical programming will be performed using statistical analysis system (SAS) version 9.3 or higher.

4.1 Analysis Populations

4.1.1 Intent-to-Treat Population

[figure not shown]
All subjects who are randomized will be included in the Intent-to-Treat (ITT) population. All planned statistical analysis will be done on the ITT population. This is the primary analysis for the study.

4.1.2 Modified Intent-to-Treat Population

All subjects who received the study treatment (daxibotulinumtoxinA for injection or placebo) will comprise the modified ITT population (mITT), and will be grouped according to each subject's randomization assignment.

4.1.3 Per Protocol Population

The Per-Protocol (PP) population will include subjects from the mITT population who do not have any major protocol violations.

[REDACTED]

[REDACTED]

[REDACTED]

[REDACTED]

[REDACTED]

4.1.4 Safety Population

All subjects who are randomized, receive treatment, and have provided at least one post-treatment safety assessment will be included in the Safety population. The summaries will be by documented treatment actually received.

4.2 Subject Disposition

The number and percentage of patients who have signed informed consent, been randomized, received treatment, and completed key visits will be tabulated by treatment group overall and by trial center (or pooled center, as appropriate) and included in a listing. Reasons for not completing the study will also be tabulated by treatment group and overall and by trial center using numbers and percentages; this data will also be included in a listing. For those patients who are considered to have failed screening, the reason(s) for failure will be provided in a listing.

The number and percentage of patients included and excluded from the analysis populations (ITT, PP and safety) will be tabulated overall and for each treatment group. Reason(s) for exclusion from each population will be summarized and listed.

[REDACTED]

[REDACTED]

[REDACTED]

[REDACTED]

Major protocol deviations will be listed and summarized by treatment group.

4.3 Demographic and Baseline Characteristics

Descriptive statistics will be used to summarize demographic and baseline characteristics by treatment group and overall. Continuous variables will be summarized using the number of non-missing observations, mean, standard deviation, median, minimum and maximum. Categorical

data will be summarized using the number and percentage of patients in each category. Demographic data include age, sex, race and ethnicity. Age in years will categorized as <30, 30-
<40, 40 to <50, 50 to <60, and >=60 for summarizing by treatment group and overall. Baseline characteristics include the Foot and Ankle Physical Examination assessments of the efficacy questionnaires: AOFAS, FADI, PROMIS, and PFPS. Summaries will be produced for the ITT and PP populations by randomized treatment; and, selected summaries will be produced for the Safety population by actual treatment received.

4.4 Medical History

Medical history will be classified on the basis of MedDRA terminology, using the latest terminology at the time of database finalization. Medical history will be summarized by treatment group, system organ class, and preferred term, and will be listed.

4.5 Prior and Concomitant Medications

Prior therapies/medications recorded at Screening but no longer being taken, and concomitant therapies/medications recorded at Screening and still being taken or being taken at each trial visit, will be coded using the World Health Organization (WHO) drug dictionary and summarized by treatment group and overall, Anatomical Therapeutic Chemical (ATC) second level term, and preferred name for the Safety population. Prior and concomitant medications will be summarized separately.

4.6 Efficacy Analyses

Data listings and descriptive statistics will be produced for all endpoints at all timepoints by treatment group.

4.6.1.1 Primary Endpoint

The change from baseline in the VAS for pain for the affected foot at Week 8, in the ITT Population is the primary endpoint. [REDACTED]

4.6.1.4 Sensitivity Analyses

As a sensitivity analysis to check the impact of major protocol violations on study results, the primary and secondary efficacy outcome measures will also be analyzed on observed data from all subjects in the per-protocol (PP) population. As well, to check the robustness of results using the LOCF approach, analysis using multiple-imputation for the missing data on ITT population

will be used as sensitivity analysis. Thus, each primary and secondary endpoint will have two additional sensitivity analyses.

[REDACTED]

[REDACTED]

[REDACTED]

[REDACTED]

4.7 Safety Analyses

Safety summaries and analyses will be performed on the Safety population. Descriptive statistics will be presented to summarize the safety data.

4.7.1 Extent of Exposure

All subjects receive one administration of investigational product. The total volume of investigational product injected and the volume of investigational product injected at each of the injection sites will be summarized using descriptive statistics (number of observations, mean, standard deviation, median, minimum, maximum).

4.7.2 Adverse Events

All information pertaining to AEs noted during the trial will be listed by subject, detailing the verbatim description given by the Investigator, preferred term, system organ class, start date, stop date, severity, action taken regarding study drug, corrective treatment, outcome, and drug relatedness. The event onset will also be shown relative (in number of days) to the date of first study treatment administration. In addition, a list of subjects who prematurely discontinue from the trial due to adverse events will also be provided.

All treatment-emergent AEs (TEAEs) will be listed and summarized by treatment group, system organ class, preferred term, severity, relationship, and seriousness. Also, serious AEs (SAEs) will be summarized by treatment group, severity, and relationship to study treatment. For summaries, each subject will be counted only once within a system organ class or a preferred term using the event with the greatest relationship or highest severity.

Comparisons between treatment groups will be made by tabulating the frequency of subjects with one or more TEAEs from baseline (post-treatment) to Week 8, as well as from baseline (post-treatment) through the duration of the trial.

[REDACTED]

[REDACTED]

[REDACTED]

The injection site evaluations will be summarized using number and percentage of subjects reporting the presence of each item by treatment group and visit. In addition, the number and percentage of subjects reporting any injection site item will be summarized by treatment group overall, and by visit.

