6.6.1 RESCUE MEDICINE

The Sponsor will not allow any type of rescue medication in this clinical study for the treatment of plantar fasciitis. Subject(s) may withdraw from the study at any time if rescue medication is required.

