3.1 Study Design

The study is designed as a phase 2, prospective, randomized, placebo-controlled, double-blinded clinical trial to compare daxibotulinumtoxinA for injection and placebo injections for the management of plantar fasciitis signs and symptoms.

Approximately 60 subjects, from 5 sites in the United States, 18-65 years of age, [REDACTED]

[REDACTED]

[REDACTED]

[REDACTED]

[figure not shown]
The study duration for each participant is up to approximately five (5) months (up to four [4] weeks for Screening, a single Injection day, and up to 16 weeks of Follow-up). [REDACTED]

[figure not shown]
[REDACTED]

[figure not shown]
[REDACTED]

[REDACTED]

A participant is considered to have completed the study if he or she has completed all visits of the study including the last visit or the last scheduled procedure (See Table 3.1-1 for the complete schedule of assessments). The end of the study is defined as completion of the last visit or procedure in the trial globally.

[figure not shown]

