3.1.1 Determination of Sample Size

With a total of 60 subjects (30 per group) and assuming a drop-out rate of no more than 20%, [REDACTED]

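### The visible between-arm TEAE comparison takes no account of time observed, so drop-out that differs by arm could bias it modestly; follow-up time and a Kaplan-Meier estimate belong beside it

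*SAP*

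**What the plan says.** SAP 4.7.2 sets the between-arm comparison: "Comparisons between treatment groups will be made by tabulating the frequency of subjects with one or more TEAEs", over two windows, "from baseline (post-treatment) to Week 8, as well as from baseline (post-treatment) through the duration of the trial". The denominator is the Safety population of SAP 4.1.4: subjects randomized and treated who have at least one safety assessment after treatment. A subject seen once therefore counts the same as a 16-week completer.

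Four other statements matter.

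- Exposure and schedule are equal by design. SAP 4.7.1: "All subjects receive one administration of investigational product". SAP 3.1: "a single Injection day, and up to 16 weeks of Follow-up".
- Safety is descriptive. SAP 4.7: "Descriptive statistics will be presented to summarize the safety data". No test, alpha or margin for AEs is visible.
- Drop-out is expected. SAP 3.1.1 plans for 60 subjects, 30 per group, "assuming a drop-out rate of no more than 20" per cent. This is one overall ceiling, not split by arm.
- Protocol 6.6.1 bars rescue medication for plantar fasciitis and adds: "Subject(s) may withdraw from the study at any time if rescue medication is required".

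The only visible timing information on AEs is in the listings: "The event onset will also be shown relative (in number of days) to the date of first study treatment administration". The visible text has no person-time rate, time-to-first-event summary or AE follow-up time by arm. SAP 4.7.1 summarizes injected volume, not time observed.

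**The concern.** A crude proportion treats a subject who leaves at Week 3 without an event as event-free for the whole window. If both arms lose subjects alike, both proportions are somewhat too low and the difference between them is unaffected when true risk is equal. If one arm loses more subjects before a first TEAE, its proportion falls further and a difference appears that is not real.

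The no-rescue rule gives a documented route to such imbalance, since leaving can depend on pain relief and so on arm. Safety is named with efficacy in the primary objective (Protocol 3, SAP 2.1), and this table is the visible between-arm AE comparison. At stake is whether a small excess in that table reflects the product or retention.

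**Working it through.** **Plan's own figure.** The plan states no figure for the AE comparison. The sample size cannot be reproduced because its inputs are redacted; 24/(1 - 0.20) = 30 shows only that 30 per group is consistent with 24 completers.

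**Inputs.** From the documents: 30 per arm, 20% overall drop-out ceiling, windows of 8 and 16 weeks, and capture of non-serious AEs for 7 days after participation ends (Protocol 8.4.4). Assumed, because the documents do not give them: the same true 16-week TEAE risk p in both arms, 30-50%; exits of 30% on placebo and 10% on active, averaging 20%; exit unrelated to AEs within an arm; exit times uniform over Weeks 1-8 or Weeks 1-16.

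**Formula.** Let H(t) be the cumulative TEAE hazard, with H(16) = -ln(1 - p), and S(t) = exp(-H(t)). For an arm with exit fraction d and window T, the crude proportion is 1 - [(1 - d)S(T) + dA]. A is the mean of S at the end of observation among leavers, capped at T. The gap, active minus placebo, is (0.30 - 0.10)(A - S(T)).

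**Worked case.** p = 40%, constant hazard, exits over Weeks 1-8:

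- h = -ln(0.60)/16 = 0.0319 per week
- A = (e^(-h) - e^(-8h))/(7h) = 0.868
- Placebo: 1 - (0.70 x 0.60 + 0.30 x 0.868) = 32.0%
- Active: 1 - (0.90 x 0.60 + 0.10 x 0.868) = 37.3%
- Gap: 0.20 x (0.868 - 0.60) = 5.4 points

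With 7-day post-exit capture, A = 0.841 and the gap is 4.8 points. With exits spread over Weeks 1-16 instead, A = 0.770 and the gap is 3.4.

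**Range for p = 30-50%, gap in points.** Front-loaded means half the cumulative hazard in Week 1 and half spread evenly: H(t) = H(16) x [0.5 min(t, 1) + 0.5 t/16].

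| Hazard | Exits | 7-day capture | Through Week 16 | To Week 8 |
|---|---|---|---|---|
| Constant | Weeks 1-8 | no | 4.1-6.5 | 1.4-2.4 |
| Constant | Weeks 1-16 | yes | 2.3-3.5 | 0.5-0.8 |
| Front-loaded | Weeks 1-8 | no | about 2-3 | about 0.6-1 |
| Front-loaded | Weeks 1-16 | yes | 1.1-1.6 | 0.2-0.3 |

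**Second model.** Take exponential drop-out reaching 30% and 10% by Week 16, with p = 40% and constant hazard. The crude proportion is h/(h + m) x (1 - e^(-16(h + m))), with m = -ln(1 - d)/16. This gives 34.2% v 38.1%, 4.0 points before rounding, and 1.3 points to Week 8. If the hazard halves every one or two weeks, the gap is 0.7-1.4 points in either window.

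**Scale.** The gap is proportional to the difference in exit fractions: zero at 20% v 20%, half as large at 25% v 15%, double at 40% v 0%. In subjects, 1-6.5 points of 30 is 0.3-2. The standard error of the difference is sqrt(2p(1 - p)/30): 11.8 points at p = 30%, 12.6 at 40% and 12.9 at 50%.

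**The case against.** The strongest reply is that a count of subjects with at least one TEAE correctly describes what was observed, and is a usual summary for a short single-dose trial with no formal safety inference. That stands, and it is why the crude table should remain.

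The plan also limits the problem. Leavers are asked back for the Week 16/Early Termination assessments where possible (Protocol 7.2). AEs are recorded for 7 days, and SAEs for 30, after participation ends (Protocol 8.4.4). Staff try to collect data by telephone or mail from subjects who will not return (Protocol 10.1.9.3). Completion of key visits and reasons for leaving are tabulated by arm (SAP 4.2). The Week 8 window is already specified. These measures reduce the gap and would reveal unequal loss, but they do not adjust the TEAE proportions.

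A reader might infer three stronger things that the documents do not support.

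- *Follow-up is unequal as planned.* It is equal by design and differs only through drop-out, for which no arm-specific figure is given.
- *The table makes the active product look safer than it is.* The one documented mechanism, withdrawal for lack of relief, points to placebo loss and the opposite direction. Subjects who leave because of a recorded TEAE are already counted. Hidden harm would need excess active-arm exits before a first event, for which the documents give no route.
- *The SAP contains no follow-up-adjusted AE analysis.* Three blocks directly after the quoted comparison are redacted, so this cannot be known.

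The reply that the gap lies within sampling error is right about size. It does not dispose of the point, because this error is systematic and cannot be seen in the TEAE table itself.

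**Conclusion.** The point holds as a minor one. The visible TEAE comparison can be biased, but only if drop-out before a first TEAE differs by arm. With 30% v 10% exits and a true 16-week risk of 30-50%, the spurious difference is about 1-6.5 points through Week 16 and about 0-2.4 points to Week 8. The upper figures need a constant hazard for 16 weeks after one injection, all exits by Week 8 and no post-exit capture. Even they are about half the standard error of 12-13 points. A 40% v 0% split would double them, but requires every exit to fall in one arm.

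TEAE risk, hazard shape, exit timing and the split by arm are all assumptions. The through-trial window is the one worth protecting; the Week 8 comparison is little affected.

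**What to change.** In SAP 4.7.2, keep the crude frequency table for both windows and add one panel beside it showing:

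1. subject-weeks of AE follow-up by arm;
2. the Kaplan-Meier cumulative incidence of first TEAE at Week 8 and Week 16 by arm, censored at the last visit or AE contact.

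State in advance that the Kaplan-Meier estimate will be used to interpret the through-trial comparison if follow-up differs by arm. Define the censoring date so that it agrees with the 7-day post-exit capture of non-serious AEs. If a redacted paragraph already provides such a summary, a cross-reference is enough.

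The cost is a few lines of SAP text and one table panel, with no change to trial conduct. Onset days and visit dates are already planned; a separate date of last AE contact is not named in the visible text, so the last visit is the fallback. The statistical price is the assumption that exit within an arm is unrelated to AE risk. That cannot be verified, but it is more plausible than reading the crude count as a 16-week risk, which supposes that no leaver would have had a later first event.

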4.7.3 Laboratory Tests

Laboratory test results, actual values and change from screening values, will be summarized with descriptive statistics (number of non-missing observations, mean, standard deviation, median, minimum and maximum) for each treatment group at Screening, Visit 4 (Week 2), and the Final Evaluation Visit. Categorical laboratory test results will be summarized using number and percentage of subjects in each category for each treatment group at Screening, Visit 4 (Week 2), and the Final Evaluation Visit.

Shift tables (low, normal, high) will be presented to summarize laboratory test results at Screening and the Final Evaluation Visit. Normal ranges established by the central laboratory will be used to determine shifts.

Urine pregnancy tests will be presented in data listings only.

[REDACTED]

[REDACTED]

[REDACTED]

[REDACTED]

[REDACTED]

[REDACTED]

[REDACTED]

[figure not shown]

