Height, Weight, Vital Signs: Height will be collected only at the Screening visit. Weight and vital signs (i.e., body temperature, respiration rate, sitting radial pulse rate, and sitting systolic and diastolic blood pressures) will be obtained at the Screening, Injection Visit (pre- and post-treatment), Weeks 1, 2, 4, 8, and 16/Early Termination visits and at any visit where signs or symptoms of botulinum toxicity is reported.

12-Lead Electrocardiograms (ECGs): At Screening, Week 2, and Week 16/Early Termination, a single standard supine 12-lead ECG will be obtained after a subject has rested quietly for at least 10 minutes. The ECG data will be submitted to a central reader for measurement. Instructions for the collection, transmission, and archiving of the ECG data is outlined in the ECG central reader manual. The analyzed ECG data will be reviewed and signed by the Investigator.

X-rays: X-rays of the affected foot is collected at Screening or prior to Injection visit. This procedure is to be done at individual study site. If subject(s) have had X-ray done within six (6) months prior to the

Injection visit, this procedure is not required. Records of the X-ray is to be collected and kept with the subject’s study information.

Biological specimen collection and laboratory evaluations: As outlined in the Clinical Laboratory Tests table below, non-fasting samples for hematology, chemistry, and urinalysis will be collected at Screening, Week 2, and at Week 16/Early Termination visits. [REDACTED] will be collected at Screening and Week 16/Early Termination visits.

[REDACTED] Blood and urine will be collected using applicable safety precautions and will be processed according to the local clinical laboratory’s instructions.

Clinical Laboratory Tests

| Hematology | Chemistry | Urinalysis | Additional Tests |
|--------------------------------|--------------------------------|------------------|------------------|
| Hemoglobin | Glucose | Specific gravity | [REDACTED] |
| Hematocrit | Total bilirubin | pH | [REDACTED] |
| Leukocyte count (total) | Alanine aminotransferase | Glucose | [REDACTED] |
| Leukocyte count (differential) | Aspartate aminotransferase | Protein | [REDACTED] |
| Red blood cell count | Alkaline phosphatase | Blood | [REDACTED] |
| Platelet count | Blood urea nitrogen | Bilirubin | [REDACTED] |
| | Pregnancy (WOCBP at Screening) | Ketones | [REDACTED] |
| | Sodium | | |
| | Potassium | | |
| | Chloride | | |
| | CO2 | | |

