| | Creatinine | | |
| | Calcium | | |
| | Protein | | |

It is the Investigator’s responsibility to review the results of all laboratory tests as they become available. For each laboratory test result outside the reference range, the Investigator must ascertain if the abnormal lab result is a clinically significant result for that individual subject. Likewise, if laboratory tests are taken at follow-up visits, the Investigator must ascertain if this is an abnormal and clinically significant change pre-treatment for that individual subject. The Investigator may repeat the laboratory test or request additional tests to verify the results of the original laboratory test. The Investigator must sign and date all written laboratory results (e.g., urinalysis, hematology, chemistry, and pregnancy tests) and note Not Clinically Significant (NCS) or Clinically Significant (CS) for each out of range laboratory value. Toxicity grading for laboratory results is standardized using the FDA’s “Guidance for Industry: Toxicity Grading Scale for Health Adult and Adolescent Volunteers Enrolled in Preventive Vaccine Clinical Trials” dated September 2007. If a laboratory value is determined to be a clinically significant result for that subject, this may be considered an AE to be assessed according to severity. Refer to Section 8.4 for further information.

[REDACTED]

Injection Site Evaluation: The injection sites will be evaluated at Injection Visit (Day 0) pre- and post-treatment (to determine if there is an immediate reaction to the investigational product), follow-up visits (Weeks 1, 2, 4, 8 and 16 or Early Termination visit, if applicable. The assessment will be done as a global evaluation of the injection sites.

Injection Site Evaluation

| Assessment Descriptor | Present? | |
|---|----------|----|
| | Yes | No |
| Erythema | | |
| Edema | | |
| Burning or Stinging (sensation as described by subject) | | |
| Itching (sensation as described by subject) | | |
| Bruising | | |
| Drainage | | |

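### The planned laboratory shift tables leave out Week 2, so a low or high shift that resolves by the final visit is not counted in them

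*SAP*

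**What the plan says.** Laboratory samples have three scheduled times. SAP 3.2.2.2 places them "at Screening, Weeks 2 and 16/Early Termination visits", and Protocol 8.3 agrees: samples "will be collected at Screening, Week 2, and at Week 16/Early Termination visits".

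SAP 4.7.3 plans three kinds of laboratory output:

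- Continuous results: "Laboratory test results, actual values and change from screening values, will be summarized with descriptive statistics", at Screening, Week 2 and the Final Evaluation Visit. The statistics are n, mean, SD, median, minimum and maximum.
- Categorical results: number and percentage of subjects "in each category for each treatment group at Screening, Visit 4 (Week 2), and the Final Evaluation Visit".
- Shift tables: "Shift tables (low, normal, high) will be presented to summarize laboratory test results at Screening and the Final Evaluation Visit".

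The third sentence names two visits where the first two name three.

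**The concern.** Each subject has one injection and, by schedule, two later laboratory samples. Week 2 is nominally day 14 and Week 16 is day 112 (16 × 7), so the two are 98 days apart. An effect of a single dose on a laboratory value could appear at the first and be gone by the second.

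A shift table counts, by arm, how many subjects moved from one reference-range class to another, and the count does not depend on anyone's view of clinical importance. If it uses only the last sample, it cannot count a change that came and went. Comparing safety with placebo is part of the stated primary objective (Protocol section 3; SAP 2.1), so the early sample should be available in this form.

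**Working it through.** The laboratory section states no figure that could be reproduced. Of the sample-size inputs, only 60 subjects (30 per group) and a maximum drop-out of 20% are visible. The check is therefore a comparison of the text, followed by illustrative arithmetic.

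**1. Visits used by each output in SAP 4.7.3**

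| Output | Screening | Week 2 | Final Evaluation |
|---|---|---|---|
| Continuous values and change | yes | yes | yes |
| Categorical results, n and % | yes | yes | yes |
| Low/normal/high shift tables | yes | **no** | yes |

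**2. One subject followed through the outputs.** Take a subject who is normal at Screening, high at Week 2 and normal at the final visit.

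- Shift table: entered as normal to normal.
- Continuous summary: the value feeds into the Week 2 mean, SD and range, but the subject is not counted as having crossed a limit.
- Categorical summary: this most naturally covers tests with categorical results, such as dipstick urinalysis. Even if it covered low/normal/high classes, it gives totals per visit and not within-subject change. For example, if 3 of 30 subjects are high at Screening and 3 of 30 at Week 2, the number newly high at Week 2 could be 0 (the same three) or 3 (three others).
- Adverse event tables: the subject appears only if the investigator judges the change clinically significant.

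**3. How many subjects could be affected.** Let n = 30 treated subjects in one arm, all sampled at Week 2, and let p be an *assumed* rate of Week 2 shifts that resolve by the final visit. The documents give no such rate.

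Expected number = n × p. Probability of at least one = 1 − (1 − p)^n.

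| Assumed p | Expected (30 × p) | P(at least one) |
|---|---|---|
| 5% | 1.5 | 0.785 |
| 10% | 3 | 0.958 |
| 20% | 6 | 0.999 |

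By definition, none of these subjects is counted as shifted in a Screening-to-final table.

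**4. What the Week 2 statistics would show.** As a hypothetical case, suppose ALT rises by 60 U/L in 3 of 30 subjects and the mean change in the rest is zero. The mean moves by 3 × 60 / 30 = 6 U/L, and the maximum change is at least 60 U/L. If only one subject rose by that amount, the mean would move by 1 × 60 / 30 = 2 U/L. If nobody else rose further, the maximum change would be 60 U/L in both cases. The statistics therefore give a signal, but not the number of subjects.

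**5. Early-termination samples.** The visible SAP does not define the Final Evaluation Visit. Protocol 7.2 places early discontinuation before the Final Evaluation, yet sends those subjects to the combined Week 16/Early Termination assessments. If their samples are included, the column mixes times since injection. If they are excluded, early discontinuers have no post-treatment entry in the shift table, even when they gave a Week 2 sample. At the planning maximum this concerns 0.20 × 60 = 12 subjects, or 6 of 30 per group. For included samples, reaching 12 would also need every drop-out to return for that visit, which Protocol 7.2 asks for only where possible.

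**The case against.** The strongest reply is that Week 2 is not ignored. Values and changes from Screening are summarised at Week 2 with minimum and maximum, so a marked rise would be seen. There is also a route for individual subjects. Protocol 8.3 has the investigator classify every out-of-range value as clinically significant or not. Protocol 8.4.1 makes clinically significant post-treatment changes reportable as adverse events. SAP 4.7.2 lists events with start and stop dates and tabulates subjects with treatment-emergent events by arm, to Week 8 and over the whole trial. Laboratory safety is descriptive, with no test or decision rule attached.

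Most of this stands. A reader might infer that transient laboratory effects go unreported, and the documents do not support that: the omission is confined to the shift tables. What the reply leaves open is the count of subjects with out-of-range Week 2 values judged not clinically significant. The adverse event route is also less firm than it looks, because Protocol 8.3 says only that a significant laboratory result may be considered an adverse event, while 8.4.1 makes reporting mandatory.

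A reader might also infer that early-termination samples are pooled with Week 16. The shared visit label makes that plausible, but it is not established. Protocol 7.2 points the other way, and the redacted text after the laboratory paragraph and in SAP 4.8.4 could hold the rule. Nor would pooling earlier samples necessarily hide a transient effect; it could make one more visible.

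Finally, Protocol 8.3 says "Toxicity grading for laboratory results is standardized using" an FDA toxicity scale. A reader might take the low/normal/high table as a departure from this. It is not: the protocol standardises the grading and, in the visible text, promises no table of grades.

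**Conclusion.** The point holds for the shift tables. As written in SAP 4.7.3, they cannot count subjects whose low/normal/high shift at Week 2 has resolved by the final visit, and no other visible output supplies that count in full. The omission is plain from the visible text. Its size is not known: the 1.5 to 6 subjects per arm of 30 rest on assumed rates of 5% to 20%, and the ALT case is hypothetical.

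The lack of a definition for the Final Evaluation Visit is a secondary matter of clarity, bounded by 12 of 60 subjects at the planned maximum drop-out. It is subject to whatever the redacted text says.

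This is a modest gap in safety reporting. It is worth closing because safety against placebo is part of the primary objective and the remedy is cheap. The Week 8 pain analysis is not affected.

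**What to change.** In SAP 4.7.3, add low/normal/high shift tables by treatment group:

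1. from Screening to Week 2;
2. from Screening to the worst post-treatment value, including the repeat tests that Protocol 8.3 allows. For analytes that can be abnormal in either direction, show lowest and highest separately.

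Keep the existing Screening-to-final table. Add one sentence defining the Final Evaluation Visit and saying whether early-termination samples enter it. If they do, assign them by study day or show them separately; if the rule already exists in redacted text, a cross-reference is enough. A column of toxicity grades in the worst-value table is optional.

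The cost is a few extra table shells and their programming, from data already collected. No new samples, visits or procedures are needed.
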